	
Primary Efficacy Analysis
 
The primary endpoint will be analyzed by computing the Pearson (product-moment) and Spearman (rank) correlation between the TUV_{joint} for the biopsied joint and 2 measures of macrophage prevalence:
 
• The fraction of CD206-expressing macrophages visible in the microscope field under 4x and 10x power magnification, measured as the area fraction (AF) $AF = \frac{\text{Total Stained Area}}{\text{Total Field Area}} \times 100\%.$ 
• The volume of synovial tissue in the biopsied joint derived from the ultrasound synovitis score (Vol). The final CD206-expressing macrophage count is defined as the product of Vol and AF defined above. 
A 95% confidence interval for the population correlation coefficient measuring the association between TUV and CD206 expression (as measured via IHC) will be computed using the Fisher's Z-transformation method ($Z = \tanh^{-1} r$) and its asymptotic Normal approximation. Statistical summaries of the marginal distributions of TUV_{joint} and CD206 macrophage count will be provided (mean, standard deviation, number of cases, median, and range).
 
Secondary Efficacy Analyses
 
The degree of co-expression of CD68, CD163, and/or CD206 macrophage types will be assessed by calculating the Pearson (product-moment) correlations and Spearman rank correlations among these variables. The marginal distributions will be summarized by calculating the mean, standard deviation, number of cases, median, and range for each variable.
 
The ability of TUV_{joint} to discriminate among lympho-myeloid, diffuse myeloid, and pauci-immune fibroid types will be assessed by fitting a multinomial logistic regression model with RA pathotype as the response variable and TUV_{joint} as the explanatory variable. ROC curves will be generated for the multinomial logistic model using the lympho-myeloid type as the base class. No inferential statistics will be generated for this endpoint.

--	---

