9.4 Sample Size and Justification

The sample size is expected to be approximately 12 to 24 joints. The final sample size will be determined after the completion of an interim analysis including at least 4 subjects in each pathotype (diffuse myeloid, lympho-myeloid and pauci-immune fibroid). The final sample size will be chosen on the basis of the sponsor's business requirements regarding precision for the estimated correlation between CD206 expressing macrophage density and TUV_{joint}. The final sample size will be at least N = 12. If the rarest pathotype has 25% prevalence in the study patient pool, the expected number of subjects at the interim analysis is N = 16. These needs may be further increased because synovial biopsy fails to recover enough tissue for histological analysis in about 15% of cases ([Wechalekar 2014](#)).

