9.5.3.2 Secondary Endpoints

Co-expression of the CD68, CD163, and CD206 markers will be analyzed by 2 methods. First, by providing the product-moment and Spearman rank correlation matrices of the IHC field measurements (that is, the fraction of macrophages expressing the markers will not be multiplied by the synovitis score). Summary statistics of the data triplets used to calculate the correlation matrices will be provided (number of data triplets, means, standard deviations, minima, medians, and maxima). In the second method, histological sections will undergo immunofluorescent staining for the 3 markers and DAPI. For each section evaluated, up to 50 cells from the synovial sublining will be identified for each of the 3 markers. For each identified cell (up to 150/section), the rate of co-expression of the 3 markers will be determined. For sections with sparse marker expressing cells, four microscope fields will be randomly selected. Co-expression of the markers will be quantified for any cell observed expressing any marker.

The ability of TUV_{joint} to discriminate among lympho-myeloid, diffuse myeloid, and pauci-immune fibroid RA disease types will be evaluated with a multinomial logistic regression

model with TUV_{joint} as a covariate. RA type will be the response variable and TUV_{joint} will be the explanatory variable. ROC curves will be generated using the lympho-myeloid type as the base class. The marginal distribution of disease type will be summarized with a frequency table, while the marginal distribution of TUV_{joint} will be summarized with descriptive statistics (number of data pairs, mean, standard deviation, minimum, median and maximum). The joint distribution will be graphically summarized with box plots showing the conditional distribution of TUV_{joint} for each disease type.

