RA type will be the response variable and  $TUV_{global}$  will be the explanatory variable. ROC curves will be generated using the lympho-myeloid type as the base class. The marginal distribution of disease type will be summarized with a frequency table, while the marginal distribution of  $TUV_{global}$  will be summarized with descriptive statistics (number of data pairs, mean, standard deviation, minimum, median and maximum). The joint distribution will be graphically summarized with box plots showing the conditional distribution of  $TUV_{global}$  for each disease type.

If it is found (based on the ROC curves from the multinomial logistic regressions) that  $TUV_{joint}$  and  $TUV_{global}$  can discriminate between the three RA disease types, then no additional analyses will be performed. However, if this is not the case, then two binary logistic regression analyses, with fibroid vs. non-fibroid disease type as the response and  $TUV_{joint}$  and  $TUV_{global}$  as predictors, respectively, will also be conducted.

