54	ECG Parameters Descriptive Statistics (Safety Population)	X	X
55	Summary of Treatment Emergent Adverse Events (Safety Population)	X	X
56	Number and Percent of Subjects with TEAEs (Safety Population)	X	X
57	Descriptive Statistics of $TUV_{joint}$ by Fibroid vs. Non-Fibroid Type (ITA Population)	X	X
58	Descriptive Statistics of $TUV_{joint}$ by Fibroid vs. Non-Fibroid Type (PP Population)	X	
59	Descriptive Statistics of $TUV_{global}$ by Fibroid vs. Non-Fibroid Type (ITA Population)	X	
60	Descriptive Statistics of $TUV_{global}$ by Fibroid vs. Non-Fibroid Type (PP Population)	X	

Figure No.	Figure Title	Included in Final Figures	Shown in Appendix B
Fig1	Scatterplot of the Joint Distribution of CD206 Macrophage Count and $TUV_{joint}$	X	X
Fig2	Boxplots of the Conditional Distribution of $TUV_{joint}$ for Each Category of Synovitis Score	X	X
Fig3	Boxplots of the Conditional Distribution of $TUV_{global}$ for Each Category of Synovitis Score	X	
Fig4	ROC Curves by RA Disease Type, Logistic Regression with $TUV_{joint}$	X	X
Fig5	ROC Curves by RA Disease Type, Logistic Regression with $TUV_{global}$	X	
Fig6	Conditional Distribution of $TUV_{joint}$ by RA Disease Type	X	X
Fig7	Joint Distribution of CD3, CD20, CD55, CD68, CD163, CD206, and TE7 Biomarkers Association with $TUV_{joint}$	X	X
Fig8	Joint Distribution of CD68, CD163, and CD206 in mRNA	X	X
Fig9	Joint Distribution of CD68, CD163, and CD206 Measured by Flow Cytometry	X	X

Data Listing No.	Data Listing Title	Included in Final Listings	Shown in Appendix B
DL1	Subject Disposition Data Listing	X	X
DL2	Inclusion/Exclusion Data Listing	X	X
DL3	Protocol Deviations Data Listing	X	X
DL4	Demographics Data Listing	X	X
DL5	Subjects Excluded from ITA Population Data Listing	X	X
DL6	Subjects Excluded from PP Population Data Listing	X	X
DL7	Subjects Excluded from Safety Population Data Listing	X	X
DL8	Medical History Data Listing	X	X
DL9	Prior and Concomitant Medications Data Listing	X	X
DL10	Prior and Concomitant RA Medications Data Listing	X	X
DL11	Adverse Events Data Listing	X	X
DL12	Occurrence of TEAEs Associated with Concomitant Medications or Class of Medications	X	X
DL13	Subject Laboratory Profiles – Hematology Data Listing	X	X
DL14	Subject Laboratory Profiles – Serum Chemistry Data Listing	X	
DL15	Subject Laboratory Profiles – Urinalysis Data Listing	X	
DL16	Subject Laboratory Profiles – Rheumatology Panel Data Listing	X	
DL17	Physical Exam Data Listing	X	X
DL18	ACR/EULAR 2010 Classification Data Listing	X	X

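### The decision on whether TUV discriminates pathotypes is read from ROC curves whose direction is fitted to the same 12 to 24 joints, so an uninformative TUV still gives an expected area of about 0.58 to 0.67

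*Protocol*

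**What the plan says.** Protocol 9.5.3.2 and SAP 4.2.2 fit a three-class multinomial logistic model with a single covariate: "RA type will be the response variable and TUV_{joint} will be the explanatory variable". ROC curves follow, with lympho-myeloid as the base class. Protocol 9.5.3.3 and SAP 4.2.3 repeat this for TUV_global.

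The protocol synopsis, under both the secondary and the exploratory efficacy analyses, adds: "No inferential statistics will be generated for this endpoint".

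The last paragraph of SAP 4.2.3 nevertheless draws a yes/no conclusion. If TUV_joint and TUV_global are found, "based on the ROC curves from the multinomial logistic regressions", to separate the three types, nothing further is done. If not, two binary models of fibroid versus non-fibroid are run.

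SAP 7.0 lists the curves as Figures 4 and 5 ("ROC Curves by RA Disease Type, Logistic Regression with" TUV_joint or TUV_global). None of its 60 tables is assigned an area under the curve or an interval for one. Neither document mentions a direction fixed in advance, a hold-out set, cross-validation or a correction for optimism.

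On size, Protocol 9.4 states: "The sample size is expected to be approximately 12 to 24 joints". The final number is set after an "interim analysis including at least 4 subjects in each pathotype".

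**The concern.** With one covariate, the fitted log-odds of a pathotype against lympho-myeloid is a straight line in TUV. Rescaling that line does not change a ROC curve; reversing it does. So the only feature of the fit that affects such a curve is the sign of the slope, and that sign is estimated from the joints being plotted. The curve is usually turned to the favourable side of the diagonal, and its null expectation is no longer 0.5.

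This is separate from the lack of a stated criterion for discrimination. Any criterion would be applied to an area that is centred too high.

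Two things are at stake. A chance result could be taken as support for the statement in Protocol 1.1 that imaging may separate the pathotypes. The same result would also cancel the fibroid versus non-fibroid models, the contrast for which the protocol gives the clearest biological reason.

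**Working it through.** **Inputs.** N is 12 to 24 joints, one per subject, with at least 4 per pathotype at the interim (Protocol 9.4). The documents give no pathotype split at N = 24 and no TUV distribution. I assume 8/8/8 and 9/9/6 (lympho-myeloid/diffuse/fibroid), with 10/10/4 as an extreme, and TUV either normal or lognormal.

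**The plan's own figure.** Waiting for 4 subjects of a type with 25% prevalence takes 4 / 0.25 = 16 subjects on average, which matches "the expected number of subjects at the interim analysis is N = 16". The plan states no area or precision for the pathotype endpoint, so there is nothing further to reproduce.

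**Exact check, 4 v 4.** Let U be the Mann-Whitney count and A = U/16. Under no discrimination the 70 orderings give U = 0, 1, ..., 8 with frequencies 1, 1, 2, 3, 5, 5, 7, 7, 8, and symmetrically above 8.

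- Mean |U − 8| = 2 × (8 + 7 + 12 + 15 + 20 + 15 + 14 + 7) / 70 = 196/70 = 2.8.
- If the curve is always turned upward, the expected area is 0.5 + 2.8/16 = 0.675.
- If the direction is fixed in advance, the expected area is 0.50.

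**Approximation for m v n joints.** E[max(A, 1 − A)] ≈ 0.5 + √(2/π) × √((m + n + 1)/(12mn)).

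- 4 v 4: 0.5 + 0.798 × √(9/192) = 0.673 (exact 0.675).
- 8 v 8: 0.5 + 0.798 × √(17/768) = 0.619 (exact 0.620).

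**The planned model under the null.** I fitted the three-class model to simulated TUV unrelated to pathotype (2,500 to 3,000 runs per row) and took areas on the fitting data. SD is on the log scale.

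| Split | TUV | Diffuse v lympho-myeloid | Fibroid v lympho-myeloid | One-versus-rest |
|---|---|---|---|---|
| 4/4/4 | normal | 0.67 | 0.67 | 0.65 |
| 4/4/4 | lognormal, SD 0.5 | 0.66 | 0.66 | 0.64–0.65 |
| 4/4/4 | lognormal, SD 1 | 0.65 | 0.65 | 0.64 |
| 8/8/8 | normal | 0.62 | 0.62 | 0.60 |
| 8/8/8 | lognormal, SD 1 | 0.60 | 0.59 | 0.58–0.59 |
| 9/9/6 | normal | 0.61 | 0.62 | 0.60–0.61 |
| 9/9/6 | lognormal, SD 1 | 0.59 | 0.60 | 0.58–0.60 |
| 10/10/4 | normal | 0.60 | 0.64 | 0.59–0.63 |

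The one-versus-rest column is there because SAP 4.2.2 prints the logit as π_j/(1 − π_j), which leaves open which curves are meant.

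**Chance of a good-looking curve.** The documents give no cut-off, so 0.75 is illustrative. Under the null, at least one of the two lympho-myeloid-based curves reaches it in about 53% of trials at 4/4/4 and in 15 to 19% at N = 24 (8/8/8 or 9/9/6).

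**Areas below 0.5.** The slope sign follows the means, whereas the area follows the ranks, so the two can disagree. Individual null areas against lympho-myeloid fall below 0.5 in about 5 to 10% of fits with normal TUV and in about 12 to 20% with strongly skewed lognormal TUV.

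**The case against.** The strongest defence is that the analysis is declared descriptive and is secondary or exploratory. The only planned consequence of a favourable reading is that two follow-up models are not run. No efficacy claim, sample-size step or other decision depends on it. Box plots of TUV_joint by pathotype (Figure 6) and summaries of TUV_global by type (Table 50) would also reveal a curve running in an implausible direction. This limits the weight of the point. It does not remove it, because a yes/no rule is still read from the biased curve, and box plots without an interval do not correct it.

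The images of Figures 4 and 5 are not in the text available to me, so an area may be printed on them. The table list shows only that no table carries one. A printed area would be biased in the same way.

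A reader might infer stronger claims, which do not hold:

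- **That every fitted probability is monotone in TUV and every curve is simply reflected.** This is true of log-odds against the base class. In a three-class fit the probability of a middle class can rise and then fall. One-versus-rest areas are still inflated, but reflection is not the whole explanation.
- **That areas almost never fall below 0.5.** They do so in a minority of fits that is not negligible when TUV is skewed. Skew is plausible for a ratio, and for TUV_global, where joints within normal limits contribute zero.
- **That one range of null areas applies generally.** It depends on the split, the TUV distribution and the type of curve.
- **That the documents imply a direction for all contrasts.** Protocol 1.1 supports lower uptake in the fibroid type only, since it describes high macrophage densities in both other types.

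**Conclusion.** The concern holds at moderate weight. As written, the SAP judges discrimination from in-sample curves whose direction is fitted and which carry no interval.

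Under no discrimination, curves against lympho-myeloid have an expected area of about 0.65 to 0.67 at 4/4/4 and about 0.59 to 0.62 at N = 24. One-versus-rest curves have about 0.64 to 0.65 and 0.58 to 0.61. The N = 24 ranges rest on the 8/8/8 and 9/9/6 splits; with only 4 fibroid joints, the fibroid curve stays near 0.64.

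The documents do not show that a false claim will be made. They show that a favourable curve would be weak evidence, and that it would stop the fibroid versus non-fibroid analysis.

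**What to change.** In SAP 4.2.2 and 4.2.3:

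1. Draw the fibroid ROC on TUV itself with the direction set in advance (lower TUV in pauci-immune fibroid, following Protocol 1.1). The null area then centres on 0.50 and can fall below it.
2. For diffuse myeloid v lympho-myeloid, report the area in one stated orientation, do not reflect it, and read its two-sided 95% confidence interval against 0.5.
3. Print every area with a 95% interval, exact or bootstrap. Exact is safer at these sizes, because a bootstrap interval collapses to a point when separation is complete.
4. Base the decision on discrimination in SAP 4.2.3 on these intervals, and state the rule.
5. Run the fibroid v non-fibroid models whatever the curves show.
6. Amend the two protocol synopsis sentences that rule out inferential statistics, so that they match.

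The cost is SAP wording, a small protocol change and a few lines of code. The curves will look less favourable and the intervals will be wide. At 4 v 4, complete separation has a two-sided exact probability of 2/70 = 0.029, and the next most extreme result gives 4/70 = 0.057. At N = 12, therefore, only complete separation could be distinguished from 0.5 at the two-sided 5% level.

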ACR/EULAR	American College of Rheumatology/European League Against Rheumatism
ADR	Adverse drug reaction
AE	Adverse event
AF	Area fraction
ALT	Alanine aminotransferase
ACPA	Anti-citrullinated peptide antibody
AST	Aspartate aminotransferase (SGOT)
AUC	Area under the curve
BUN	Blood urea nitrogen
bDMARD	Biologic disease modifying antirheumatic drug
CD206	Mannose-binding receptor (Ca ²⁺ -binding lectin)
CI	Confidence interval
CRF	Case report form
CRP	C-reactive protein
CRA	Clinical research associate
CRO	Contract research organization
CT	Computed tomography
CV	Coefficient of variation
DAS28	Disease activity score used with the ACR/EULAR 2010 guidelines
DMARD	Disease-modifying antirheumatic drug
DTPA	diethylenetriaminepentaacetic acid
ESR	Erythrocyte sedimentation rate
ECG	Electrocardiogram
eCRF	Electronic case report form
EU	European Union

UK	United Kingdom
FDA	Food and Drug Administration
FDG	Fluoro-2-deoxyglucose
GCP	Good Clinical Practice
Hct	Hematocrit
Hgb	Hemoglobin
HIPAA	Health Information Portability and Accountability Act
HC	Healthy control
IAP	Interim analysis plan
ICF	Informed consent form
IEC	Independent ethics committee
ICH	International Conference on Harmonisation
IHC	Immunohistochemistry
IND	Investigational New Drug
IRB	Institutional Review Board
ITA	Intent-to-assay
IV	Intravenous
JAK	Janus kinase
MedDRA	Medical Dictionary for Regulatory Activities
MCP	metacarpophalangeal joint
NSAID	Non-steroidal anti-inflammatory drug
PET	Positron emission tomography
PI	Principal investigator
PK	Pharmacokinetics
PP	Per protocol
PIP	Proximal interphalangeal
PT	Preferred term
QC	Quality control
QT	Interval from the Q wave to the end of the T wave

QTc	Corrected QT interval
RBC	Red blood cell (count)
ROI	Region of interest
RA	Rheumatoid arthritis
RF	Rheumatoid factor
RR	Reference region
RSNA	Radiological Society of North America
SAE	Serious adverse event
SAP	Statistical analysis plan
SC	Subcutaneous
SGOT	Serum glutamic oxaloacetic transaminase (AST)
SGPT	Serum glutamic pyruvic transaminase (ALT)
SJC	Swollen joint count
SUV	Standard uptake value
SUSAR	Suspected unexpected serious adverse reactions
SOC	System organ class
SOP	Standardized operating procedures
$t_{1/2}$	Mean half-life
TEAE	Treatment emergent adverse event
TJC	Tender joint count
TMF	Trial Maser File
TNF α	Tumor necrosis factor alpha
TUV	Tilmanocept uptake value
TUV _{global}	Global tilmanocept uptake value
TUV _{joint}	Joint-specific tilmanocept uptake value
VAS	Visual analog scale
Vol	ultrasound synovial thickness score
US	United States
ULN	Upper limit of normal

WBC White blood cell (count)
 λ_z Mean elimination rate constant

1 INTRODUCTION

1.1 Background and Significance

Worldwide, approximately 1 in 200 adults suffers from RA. In the US and UK, there are 1.3 million and 400,000 adults living with RA, respectively. Each year, about 130,000 Americans are newly diagnosed with RA. In the UK, the incidence of RA is 3.81/10,000 person-years ([Abhishek 2017](#)). Individuals with inadequately controlled RA have significantly shorter life expectancies and frequently become disabled, leading to reduced quality of life and severe adverse economic consequences ([Lassere 2013](#), [Uhlig 2014](#), [Verstappen 2015](#), [Michelsen 2018](#)).

It has been realized for many years that RA patients who are placed on disease-modifying antirheumatic drugs (DMARDs) soon after they develop arthritis symptoms respond much more favorably to these therapies than do patients whose initiation of DMARD therapy is delayed ([Demourelle 2012](#)). Many more of these early RA patients placed on therapy achieve disease remission than is observed in RA patients who do not initiate DMARD therapy until after they have been symptomatic for RA for 6 or more months. Furthermore, those early RA patients placed on timely therapy who do not achieve remission experience less severe disease ([Anderson 2000](#), [Nell 2004](#), [van der Linden 2010](#)). Indeed, the early diagnosis of RA affords a “window of opportunity” for the greatest probability of effective RA therapy and the possibility of disease remission ([Cush 2007](#)). This window closes 3 to 6 months after patients become symptomatic with RA. The problem is that only a portion of patients first presenting with arthritis have RA, and differentiating those patients who have RA from those who do not is challenging, leading frequently to delays in accurately identifying those patients with RA.

The realization that early diagnosis of RA is critical for delivering the most effective RA treatment led to a collaboration between the American College of Rheumatology and the European League Against Rheumatism (ACR/EULAR) that resulted in 2010 in the publication of new criteria for diagnosing RA ([Aletaha 2010](#)). The intent of the ACR/EULAR 2010 criteria was to improve the diagnosis of early RA. This intent was only partially realized. There have been numerous publications reporting the results of studies evaluating the diagnostic accuracy of the ACR/EULAR 2010 criteria for identifying early RA patients. In a meta-analysis of this literature ([Sakellariou 2013](#)), it was shown that the ACR/EULAR 2010 criteria have a 73% sensitivity and a 74% specificity for correctly identifying early RA. If the ACR/EULAR 2010 criteria are used to decide who should receive DMARD therapy, this meta-analysis indicates that over a quarter of true early RA patients would not be provided with appropriate DMARD therapy during the critical window of opportunity for an optimal response. Furthermore, a significant portion of arthritis patients who do not have RA would be prescribed DMARD therapies for which they would not receive benefit and would be exposed to possible adverse side effects of the drugs. Clearly there remains an unmet need for a more accurate means to identify early RA patients, to improve aggregate outcomes for early RA patients, and to reduce adverse drug effects and healthcare costs associated with unproductive delivery of RA therapies to individuals who do not have RA.

Basic research on the pathobiology of RA has revealed that the inflammation observed in RA is the consequence of a self-perpetuating pathological alteration in the expression and downstream signaling of a network of cytokines (Olszewski 2001, Meyer 2010). Frequently, at the center of this cytokine network is the overexpression of tumor necrosis factor alpha (TNF α) (Leizer 1990, Keffer 1991, Choy 2001, Westra 2004). Recognition of the importance of disturbances in cytokine expression and especially that of TNF α formed the underlying rationale for the development of many antibody-based biologic therapies intended to block signaling by TNF α or one of the other various inflammatory cytokines involved in RA pathology (Kalden 2002, Chen 2006, Scott 2010, Vivar 2014). Many of these cytokine-directed RA biologic therapies have been granted regulatory approval and are currently commercially available. While many RA patients have benefited from recent advances in RA therapies, problems and deficiencies remain. Among these problems and deficiencies are:

- A significant portion of RA patients do not respond to RA therapies or respond insufficiently to RA therapies to achieve therapeutic goals (Furst 2011, Salliot 2011),
- All current RA therapies are associated with adverse effects, which can be common and/or severe (Tran 2013),
- Many current RA therapies, especially the biologic therapies, are exceedingly expensive, placing an imposing burden on healthcare costs (Hresko 2018) and affordability (Heidari 2018), and
- Nearly all RA therapies lack an adequate defined diagnostic element that can facilitate choosing an individual patient's therapeutic regimen that provides the highest probability of an effective treatment response.

Quantitative assessment of CD206 positivity of inflamed synovia in RA patients is expected to remedy, at least partially, all 4 of these problems and deficiencies. Tc 99m tilmanocept is a synthetic radiopharmaceutical imaging agent that was purposefully designed to be a high affinity ligand for CD206. CD206 is highly upregulated on phenotypically activated macrophages that contribute mechanistically to the underlying pathobiology of RA. It has long been recognized that activated macrophages contribute significantly to RA pathology (Ishikawa 1976, Firestein 1990, Kinne 2007). Macrophages are common in inflamed synovial tissues when patients are first diagnosed with RA (Smolen 2018) and frequently become more numerous as the disease progresses. Activated macrophages produce most of the TNF α that, in a significant proportion of cases, drives and perpetuates the inflammatory cycle in RA (Choy 2001). In the synovial sublining of a joint affected by RA, activated macrophages are frequently the dominant cell type (Cutolo 1993, Kraan 2002, Kennedy 2011). Activated macrophages significantly contribute to the destruction of bone and cartilage through their secretion of proteases (Bresnihan 1999, Ma 2005). Furthermore, the densities of synovial membrane macrophages measured before treatment, and especially the densities of sublining macrophages, have been reported to predict future joint damage (Yanni 1994, Mulherin 1996, Vieira-Sousa 2011, Orr 2017). Not surprisingly, activated synovial macrophage numbers—but not the numbers of other immune cell types—correlate with radiographically determined joint destruction in RA (Yanni 1994, Mulherin 1996). *Thus, CD206 positivity of inflamed synovia in RA patients is expected to provide clinically significant prognostic information for RA*

patients. Another important finding is that activated macrophage numbers are reduced by effective RA therapy (Vieira-Sousa 2011), but do not significantly change over the course of at least months if a patient was given ineffective RA therapy (Baeten 2006). Also, importantly, reductions in activated synovial macrophages associated with effective RA therapy typically occur *before treatment mediated changes* in the severity of clinical symptoms can be observed (Filkova 2016). Thus, a change in activated synovial macrophage numbers is now recognized as a biomarker that provides an objective and early measure of responses to RA therapies (Smith 2001, Bresnihan 2009). In fact, a change in activated synovial macrophage numbers is considered a more accurate measure of treatment response than clinical assessments, which are highly subjective in nature and prone to observer error (Wijbrandts 2007, Bresnihan 2009, van de Sande 2012). Therefore, there is a possibility that future clinical studies may show that quantitative assessment of CD206 positivity of inflamed synovia in RA patients could be used to monitor the efficacy of RA therapies, providing physicians and patients with earlier and more objective criteria to abandon ineffective therapies and adopt alternative therapies that may be more effective. Navidea's current clinical development plan for Tc 99m tilmanocept includes Phase 2 and Phase 3 studies evaluating the safety and efficacy of Tc 99m tilmanocept imaging of RA patients initiating an anti-TNF α therapy and to provide an early indication of response to therapy in this patient population before clinical symptoms have improved. Success of this clinical trials program would provide physicians and RA patients with earlier and more objective criteria to abandon ineffective therapies and adopt alternative therapies that may be more effective.

In recent years, synovial biopsy-enabled studies have greatly increased our understanding of the pathological processes occurring within the inflamed joints of RA patients (Orr 2017). An important finding of these studies has been that the inflammatory cell compositions of RA inflamed joints can vary between patients (Townsend 2014, van de Sande 2016). The biopsy specimens obtained from different RA patients can have different numbers and densities of macrophages and monocytes, lymphocytes and lymphocyte containing structures, and fibroblast-like synoviocytes (Orr 2017). These differences in cellular composition suggest that RA inflammation can be divided into 3 pathotypes, referred to as diffuse myeloid, lympho-myeloid, and fibroid, respectively (Dennis 2014, Astorri 2015). High densities of macrophages can occur in both the myeloid and lymphoid pathotypes, whereas the fibroid pathotype is largely devoid of both macrophages and lymphoid cells. These pathotypes are not fully discrete, with some overlap occurring. However, they provide a strong basis for temporal or cytological compartmentalization in RA disease natural history.

Current studies utilizing IHC analyses of synovial biopsies are insufficient to determine the distribution of the various pathotypes in RA patients but suggest that the diffuse myeloid and lympho-myeloid pathotypes are about equally frequent in RA patients with the fibroid pathotype being less common. There is growing evidence that patients with different RA pathotypes respond differently to various therapies, holding out the possibility that determining the RA pathotype of an individual patient's RA can direct the choice of the most effective therapy for that patient (i.e., personalized RA therapy) (Dennis 2014). This is an area of ongoing active investigation in RA therapy research (Pitzalis 2013, Donlin 2018, Mandelin 2018). However, already there is significant evidence indicating that patients with a myeloid-

driven RA pathotype and/or with high densities of macrophages in their inflamed synovium respond best to anti-TNF α biologic therapy (Wijbrandts 2008, Dennis 2014), whereas patients with a fibroid pathotype do not respond significantly to anti-TNF α therapy. Although these results need to be confirmed and elaborated upon in further studies, they suggest that determination of the density of activated macrophages in the inflamed synovial membranes of patients with RA could facilitate identification of those RA patients who would most benefit from anti-TNF α therapy and/or those who would not receive benefit. Additional work in this field seeks to determine if similar associations between the efficacies of other treatments and synovial pathotypes can identify those treatments that are most effective in patients with lympho-myeloid and/or fibroid RA pathotypes. Such results, if attained, would provide a great benefit to RA patients by enabling personalized delivery of optimal treatments to all RA patients. The study to be conducted (NAV3-32) is designed to establish the correlation between Tc 99m tilmanocept localization to RA inflamed joints and the number and density of CD206 expressing cells (i.e., macrophages) in the inflamed joints as determined by IHC evaluations of synovial biopsy specimens. If this study is successful, Tc 99m tilmanocept imaging may be able to discriminate the fibroid pathotype from the myeloid and lymphoid pathotypes and may be able discriminate all 3 pathotypes from each other.

Previously generated results from clinical imaging studies conducted by Navidea and extensive peer reviewed scientific literature strongly indicate that Tc 99m tilmanocept can enable non-invasive imaging of aggregates of CD206-expressing cells associated with various pathologies using planar scintigraphy. While it has been suggested that synovial biopsy and IHC evaluations might be translatable to common rheumatological clinical practice, there are 5 reasons why quantitative assessment of CD206 positivity enabled by Tc 99m tilmanocept imaging may be preferred to synovial biopsies for evaluations of RA patients.

First, biopsy procedures usually sample a single joint. If variation exists between the pathotypes of different joints in the same patient, biopsy studies cannot detect or quantify this variation. Current RA therapies and new therapies in development are, by their designed targets, likely to be more effective against specific RA pathotypes. If pathotype variation occurs within individual RA patients, this could severely limit the ability of pathotype determination by biopsy to accurately predict treatment response. A key advantage of Tc 99m tilmanocept imaging over synovial biopsies is that Tc 99m tilmanocept imaging can provide a global quantitative assessment of all joints, providing Tc 99m tilmanocept imaging with the possibility of detecting pathotype variation without biopsies. Navidea's proposed studies will directly assess RA inflammatory variation within individual patients and provide evidence relevant to determining the extent to which pathotype variation exists within individual RA patients and the ability of Tc 99m tilmanocept imaging to detect this variation.

The second reason why Tc 99m tilmanocept imaging may be preferred to synovial biopsies for evaluations of RA patients is that synovial biopsies are only performed on patients with inflamed synovia that have expanded in volume beyond a certain grade, thereby enabling extraction of sufficient tissue to assess histologically. This could be a problem when evaluating patients in the early phase of symptomatic RA disease when high densities of activated macrophages have begun to aggregate into the inflamed synovial membrane, but the synovial

membrane may not yet have expanded (i.e., thickened) sufficiently to permit biopsy sampling. As discussed above, there is an urgent need to more accurately identify RA patients as early in the disease process as possible and place them on DMARD therapy immediately to provide these patients with their best possible therapy responses.

The third reason why Tc 99m tilmanocept imaging may be preferred to synovial biopsies for evaluations of RA patients is that, although synovial biopsy procedures typically extract 6 to 14 samples of tissue from each biopsied joint, in about 5% to 10% of cases, they do not provide tissue of sufficient quantity or quality to enable adequate histological evaluations of the inflamed synovial tissue ([Kraan 2002](#), [Pitzalis 2013](#)). It is expected that Tc 99m tilmanocept imaging would not fail to quantitatively assess the aggregation of macrophages in RA inflamed joints at this frequency.

The fourth reason is that although more than one biopsy procedure can be performed on an individual joint, there are likely to be limitations on the number of times or how often a single joint can be biopsied. Furthermore, while not discussed in the literature, repeated biopsies may alter the inflammatory microenvironment in an inflamed synovial membrane and/or induce its own inflammation or wound healing response to trauma. In any event, Tc 99m tilmanocept imaging, being non-invasive and non-traumatic, is likely to be more amenable to repeated examination and would not affect synovial inflammation through repeated biopsy related trauma. These issues may be most significant when considering evaluations of the small joints of the hands where there is a limited quantity of inflammatory tissue.

The fifth and final reason why Tc 99m tilmanocept imaging will be preferred to synovial biopsies is that performing biopsies is challenging and requires extensive training ([Mandelin 2018](#)). Synovial biopsies have only been performed in research settings and until very recently, only in Europe where adequately trained and experienced investigators reside. Training and qualifying all physicians in the US who care for RA patients to perform synovial biopsies would be a significant barrier to adoption.

Tc 99m tilmanocept quantitative imaging reliably assesses all joints, is not dependent on synovial swelling, is non-invasive and non-traumatic, and does not require extensive practitioner training. Thus, for all these reasons, Tc 99m tilmanocept imaging is expected to provide clinically predictive information about the inflammatory status of inflamed joints in RA patients that is not obtainable from synovial biopsies or will be preferred over invasive and potentially risky synovial biopsies to evaluate RA patients.

In diagnostic radiology, quantitative imaging provides a layer of clinically meaningful information beyond that of qualitative interrogation. The Radiological Society of North America (RSNA) defines quantitative imaging as “the extraction of quantifiable features from medical images for the assessment of normal or the severity, degree of change, or status of a disease, injury, or chronic condition relative to normal. Quantitative imaging includes the development, standardization, and optimization of anatomical, functional, and molecular imaging acquisition protocols, data analyses, display methods, and reporting structures. These features permit the validation of accurately and precisely obtained image-derived metrics with

anatomically and physiologically relevant parameters, including treatment response and outcome, and the use of such metrics in research and patient care.” ([RSNA 2018](#))

In nuclear medicine, the SUV (standard uptake value) is an established quantitative imaging metric for the assessment of disease-related activity across a variety of neurological, cardiovascular, oncological, and immunological conditions. For example, in ¹⁸F-labeled fluoro-2-deoxyglucose positron emission tomography (¹⁸F-FDG PET) imaging, SUV is used to measure the proliferative activity of malignant tumors in various cancers through the quantification of FDG uptake using the following parameters: r , the radioactivity activity concentration [kBq/mL] measured by the PET scanner within a region of interest (ROI), a' , the decay-corrected amount of injected radiolabeled FDG [kBq], and w , the weight of the patient [g], such that such that $SUV = \frac{r}{(a'/w)}$. ([Kinahan 2010](#))

Based on the clinical utility of SUV in ¹⁸F-FDG PET imaging, Navidea pursued the development of the TUV (tilmanocept uptake value) to quantify CD206 activity on planar gamma camera imaging. TUV considers the fundamental principles of SUV and introduces modifications to account for inter- and intra-patient variability and disease pathobiology. After the evaluation of several formula permutations, Navidea has established TUV as a metric for the measurement of joint-specific CD206 activity in RA through the quantification of Tc 99m tilmanocept uptake using the following parameters: \bar{x} , the average pixel intensity of a ROI, and B , the pixel intensity of an anatomically defined within-patient reference region, such that $TUV = \frac{\bar{x}}{RR} \times 100$. Thus, another purpose of this study will be to test the reliability and clinical utility of TUV.

